## Appendix 8: Medical History Form

Subject ID _____ Date (dd/mmm/yyyy): ____/____/____
---

### Medical History Form

Please answer the following questions about your past and current medical history.

1. Do you have a history of any significant medical problems or chronic disease requiring a physician's care?

Yes (If Yes, please list below)     No

Medical Problem	Date of Diagnosis (dd/mmm/yyyy)	Are you having trouble with this problem now?
	/ /	 Yes  No
	/ /	 Yes  No
	/ /	 Yes  No
	/ /	 Yes  No
	/ /	 Yes  No
	/ /	 Yes  No
	/ /	 Yes  No
	/ /	 Yes  No
	/ /	 Yes  No
	/ /	 Yes  No

2. Have you had trouble with or sought medical attention for (please include even if stated in Question 1).

Irregular Heart Rate	 Yes  No	
Cardiac Arrhythmia	 Yes  No	
Heart Disease	 Yes  No	

Nu-Life Solutions  
Version Date: October 30, 2017

Subject ID \_\_\_\_\_ Date (dd/mmm/yyyy): \_\_\_\_/\_\_\_\_/\_\_\_\_

Chest Pain	 Yes  No	
Heart Attack	 Yes  No	
Heart Murmur	 Yes  No	
Dizziness/ Lightheadedness	 Yes  No	
Diabetic Retinopathy	 Yes  No	
Bradycardia	 Yes  No	
Epilepsy, Seizures, or Convulsions	 Yes  No	
Aneurysms	 Yes  No	
Syncope	 Yes  No	
TIA or Stroke	 Yes  No	
Drugs or Alcohol	 Yes  No	

3. Have you had trouble with or sought medical attention for (please include even if stated in Question 1).

High Blood Pressure	 Yes  No	
Head Injury	 Yes  No	
Chronic Neck or Back Pain	 Yes  No	
Hypothyroidism	 Yes  No	 Stable  Unstable
Hyperthyroidism	 Yes  No	 Stable  Unstable
Rheumatoid Arthritis	 Yes  No	
Inflammatory Arthritis	 Yes  No	
Psoriatic Arthritis	 Yes  No	

Subject ID _____ Date (dd/mmm/yyyy): ____/____/____
---

Irritable Bowel Syndrome	 Yes  No	
Neuropathy	 Yes  No	 Motor  Sensory
Headaches	 Yes  No	 Tension  Migraine

4. **FEMALES ONLY; if male, skip to Question #5.**
- a. Are you pregnant, or trying to become pregnant?  Yes  No
  - b. Are you using birth control?  Yes  No
  - c. If 'Yes', describe:
5. Have you had any surgery in the past three months?  Yes  No  
If 'Yes', describe:
6. Have you ever been hospitalized for psychiatric reasons?  Yes  No
7. Have you ever been diagnosed with any of the following disorders?

Depression	 Yes  No	 Less than 3 months ago  3-12 months ago  Greater than 1 year ago
Bipolar Disorder	 Yes  No	 Less than 3 months ago  3-12 months ago  Greater than 1 year ago
Panic Disorder	 Yes  No	 Less than 3 months ago  3-12 months ago  Greater than 1 year ago
Phobia	 Yes  No	 Less than 3 months ago  3-12 months ago  Greater than 1 year ago

Subject ID _____ Date (dd/mmm/yyyy): ____/____/____
---

PTSD	 Yes  No	 Less than 3 months ago  3-12 months ago  Greater than 1 year ago
Obsessive Compulsive Disorder	 Yes  No	 Less than 3 months ago  3-12 months ago  Greater than 1 year ago
General Anxiety Disorder	 Yes  No	 Less than 3 months ago  3-12 months ago  Greater than 1 year ago
Schizophrenia	 Yes  No	 Less than 3 months ago  3-12 months ago  Greater than 1 year ago
Schizo-Affective Disorder	 Yes  No	 Less than 3 months ago  3-12 months ago  Greater than 1 year ago

9. Have you ever been given any medications for emotional problems, such as anti-depressant, anti-anxiety or anti-psychotic medications?  Yes  No

## Appendix 9: Treatment Form

### Weekly Treatment Form

Subject ID \_\_\_\_\_ Date (dd/mmm/yyyy): \_\_\_\_/\_\_\_\_/\_\_\_\_

1. Device Serial Number: \_\_\_\_\_

2. Was the device placed on the participant's left ear?

Yes     No    If no, reason why: \_\_\_\_\_

## Appendix 11: ePRO Questionnaires

DATE: \_\_\_\_\_  
Week # \_\_\_\_\_

Device/Pad serial # \_\_\_\_\_  
Subject ID \_\_\_\_\_

# Complete Patient ePRO Questionnaire Packet

Version Date: 07/Nov/2017

Approval Date:

**Form DQ-7: Patient Demographics**

**Subject ID**

\_\_\_\_\_

**Date (dd/mmm/yyyy):**

\_\_\_\_/\_\_\_\_/\_\_\_\_

**Age**

What is your age? \_\_\_\_\_

**Sex at Birth**

- Male
- Female
- Other
- Choose not to answer

**Marital Status**

- Single
- Married
- Divorced
- Widowed

**Primary Language?**

Self-Description (please choose one):

- Arabic
- Bengali
- English
- French
- German
- Hindi/Urdu
- Japanese
- Mandarin
- Portuguese
- Punjabi
- Russian
- Spanish
- Other

**Race/Ethnicity**

Self-Description (please choose one):

- American Indian
- Asian-American/Oriental/Pacific Islander
- Asian East Indian
- Black/African-American
- Mexican-America/Chicano
- Puerto-Rican
- Other Hispanic
- White/Caucasian
- Other

**Education History**

What is the highest degree or level of school you have completed? *If currently enrolled, highest degree received.*

- No schooling completed
- Nursery school to 8th grade
- Some high school, no diploma
- High school graduate, diploma or GED
- Some college credit, no degree
- Trade/technical/vocational training
- Associate degree
- Bachelor's degree
- Master's degree
- Professional degree
- Doctorate degree

**Service Status**

Are you now, or have you ever served as a member of the armed forces?

- Yes, I am a military veteran
- Yes, I am an active duty member
- No, I have never served in the armed forces

Are you a First Responder (firefighter, EMS, law enforcement, etc)?

- Yes, I am current or former First Responder
- No, I have never been a First Responder

Nu-Life Solutions

Version Date: November 7, 2017

Page 1 of 1

**PEG: A Three-Item Scale Assessing Pain Intensity and Interference**

Subject ID: \_\_\_\_\_ Date (dd/mmm/yyyy): \_\_\_\_/\_\_\_\_/\_\_\_\_

**PEG: A Three-Item Scale Assessing Pain Intensity and Interference**

1. What number best describes your pain on average in the past week?

0 1 2 3 4 5 6 7 8 9 10  
No pain Pain as bad as  
you can imagine

2. What number best describes how, during the past week, pain has interfered with your enjoyment of life?

0 1 2 3 4 5 6 7 8 9 10  
No pain Pain as bad as  
you can imagine

3. What number best describes how, during the past week, pain has interfered with your general activity?

0 1 2 3 4 5 6 7 8 9 10  
No pain Pain as bad as  
you can imagine

From Krebs et al., 2009.

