## PATIENTS' GLOBAL IMPRESSION OF CHANGE (PGIC) SCALE

Subject ID: \_\_\_\_\_

Date (dd/mmm/yyyy): \_\_\_\_/\_\_\_\_/\_\_\_\_

Chief Complaint (Presenting Problem): \_\_\_\_\_

Since beginning treatment at this clinic, how would you describe the change (if any) in ACTIVITY LIMITATIONS, SYMPTOMS, EMOTIONS, and OVERALL QUALITY OF LIFE, related to your painful condition? Please circle the number below, that matches your degree of change since beginning care at this clinic for the above stated chief complaint.

No change	Almost the same	A little better	Somewhat better	Moderately better	Better	A great deal better
1	2	3	4	5	6	7

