**NOTE TO HEALTH CARE PROVIDER**

A significant, favorable change is a score of 5-7  
 No significant change is a 1-4 response.  
 Note, this a dichotomous scale (5-7 = yes; 1-4 = no).  
 A 2-point change is significant from their last reported score.  
 Reference: Hurst H, Bolton J. Assessing the clinical significance of change scores recorded on subjective outcome measures. *Journal of Manipulative Physiological Therapeutics (JMPT)* 2004;27:26-35.

Subject ID \_\_\_\_\_ Date (dd/mmm/yyyy): \_\_\_\_/\_\_\_\_/\_\_\_\_

[figure not shown]

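### In the printed questionnaire packet, PEG items 2 and 3 ask about interference but carry pain-intensity anchors; a lesser point is that the PGIC stem names two referents

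*Protocol*

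**What the plan says.** Protocol section 8.1 and the SAP's Primary Endpoints both name the PEG as the pain tool and the PGIC as the quality-of-life tool for the 8-week primary effectiveness endpoint. Both documents describe these tools as validated. Protocol section 8.2 uses them again at weeks 4, 8 and 12. Patients answer on their own devices (Protocol section 4.1, footnote 3, and section 5.0). The only wording the documents give is in Appendix 11, under the title "Complete Patient ePRO Questionnaire Packet", version dated 7 November 2017.

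The pain form is headed "PEG: A Three-Item Scale Assessing Pain Intensity and Interference". Item 1 asks for average pain over the past week. Item 2 asks "What number best describes how, during the past week, pain has interfered with your enjoyment of life" and item 3 asks "What number best describes how, during the past week, pain has interfered with your general activity". The 0-10 scale under each of the three items has the same end labels. In the text as read from the PDF they run together as "No pain Pain as bad as" and finish on the next line with the worst the patient can imagine.

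The PGIC form opens with a free-text chief complaint. Its question is about change "related to your painful condition". Its answering instruction reads: "Please circle the number below, that matches your degree of change since beginning care at this clinic for the above stated chief complaint".

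**The concern.** A 0-10 item is interpretable when its end labels describe what the stem asks. In items 2 and 3 the stem asks how far pain got in the way of life or activity, while the labels describe how bad the pain is. A patient with severe pain but little interference, or the reverse, cannot tell from the form which of the two to rate. Some may follow the stem and others the labels. At stake is what the primary pain measure records for two of its three items, in a study that relies on change from baseline and has no control arm assessed under the same wording.

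The PGIC raises a similar but smaller question. Pain is not required for entry, so for some patients the condition named in the question and the complaint named in the instruction may not be the same thing.

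**Working it through.** No power or sample size figure is involved, so the check is a comparison of texts plus two counts.

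**1. PEG, stem against labels.**
- Item 1: stem asks for intensity; labels describe intensity. They match.
- Item 2: stem asks for interference with enjoyment of life; labels describe intensity. They do not match.
- Item 3: stem asks for interference with general activity; labels describe intensity. They do not match.

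The form's title treats intensity and interference as two things, so the mismatch is visible on the form itself, without recourse to the published instrument. The full label text recurs under each item, so an error in reading the PDF is unlikely, though the original page should be looked at.

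**2. Share of the PEG involved.** Three items scored 0 to 10 give a raw maximum of 3 x 10 = 30. Items 2 and 3 hold 2 x 10 = 20 of these, and 20/30 = 67%. The documents give no PEG scoring rule; the share is the same for an equally weighted sum or average.

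**3. What could happen to the change score.** Suppose a patient reads items 2 and 3 as intensity at both baseline and week 8. Those items then contribute the change in intensity in place of the change in interference. The score differs only if the two change by different amounts; if they change equally, the effect is zero. If a patient reads the items one way at baseline and the other way at week 8, the gap in level between intensity and interference also enters. The documents say nothing about how patients read the items or how far the two quantities diverge, so neither direction nor size can be derived.

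**4. Which patients.** Protocol section 5.0 limits the symptom-response analysis to each patient's stratified indication, and section 8.1 speaks of the respective stratified populations. On that text the PEG problem falls on the pain stratum. The corresponding SAP text (Study Endpoints and Data Analysis, and Primary Endpoints) does not repeat the limit.

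**5. PGIC.** The question points to a painful condition and the instruction to the recorded chief complaint. These coincide only when the chief complaint is the painful condition. Section 3.1 admits a patient with any one of the four symptoms, so a non-pain chief complaint is possible. The number of such patients is not given, and section 1.1 says the symptoms tend to cluster, so it may be small. In the PGIC row of the 12-week assessment table the patient form is marked at weeks 2 to 8 (7) and week 12 (1), 7 + 1 = 8 times. Weeks 4, 8 and 12 enter stated endpoints and week 8 is primary. The count covers that row only: the optional maintenance and follow-up table schedules more, and footnote 3 also lists the PGIC within the ePRO set, which is marked at further weeks.

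**The case against.** The strongest reply is that the evidence is a printed packet. Patients answer on screens that are not shown, and the PEG page credits an outside source form that is not available here. A slip in preparing the appendix cannot be told apart from the wording patients actually saw. Each stem also asks about interference in plain words, and the same form serves baseline and week 8, so a patient who reads it consistently may show the same change either way. All of this stands. It makes the harm conditional, but it does not make the labels fit the stems, and the packet is the only wording on record.

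On the PGIC the reply is stronger. The one instruction on how to answer names the chief complaint, the form records that complaint, and the explanation of the scores speaks neutrally of the condition. The printed split of scores into yes (5-7) and no (1-4) is a note to the health care provider; the endpoint text is framed by medians and does not adopt it. What remains is a question with two referents.

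A reader might infer that the primary pain result is biased in the device's favour, or that PGIC scores from patients without pain cannot be used. The documents support neither. They give no basis for a direction, and the PGIC instruction points to the right complaint. Nor is it a fault that the PEG combines intensity and interference; that is its stated purpose.

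**Conclusion.** The point holds for the packet as printed. Two of the three PEG items, 20 of 30 raw points (67%), have response labels that do not match their questions, in a tool named for the primary endpoint. If the live screens match the packet, answers to those items are ambiguous; the effect on the change score has unknown sign and size and may be zero. It would be tempting to say that only the pain stratum is affected. The Protocol supports that, but the SAP leaves the restriction out, so it cannot be taken as settled.

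The PGIC conflict is real but lesser. It concerns only patients whose chief complaint is not pain, in unknown number, and the answering instruction already favours the chief complaint.

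The conclusion assumes that the end labels were read correctly from the PDF. Any consequence for the data assumes in addition that the screens carry the same text.

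**What to change.** 1. Check the live ePRO screens and the source forms for the PEG and the PGIC against Appendix 11.
2. Where the mismatch is present, give PEG items 2 and 3 end labels that express degree of interference, in line with their own stems.
3. Remove the pain-specific phrase from the PGIC question so that it has one referent.
4. If either change departs from its source form, document it as an adaptation and do not assume that the description as validated carries over.
5. Record the form version for each assessment and, where possible, keep each patient on one version from baseline to week 8.
6. For data already collected on the printed wording, report PEG item 1 separately from items 2 and 3, and report the PGIC by whether the recorded chief complaint is pain. Both tables should be descriptive only.
7. State in the SAP whether the PEG analysis is limited to the pain stratum, as the Protocol has it.

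The cost is one check, up to two text corrections, one version field, two descriptive tables and a sentence in the SAP. If the screens prove correct, only the check, the correction of Appendix 11 and the SAP sentence are needed. The downside is that patients already assessed on the mismatched wording must be flagged, and any patient switched mid-study has a change score that spans two versions of the form.

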**GAD-7 - Generalized Anxiety Disorder 7-item Scale**

Subject ID: \_\_\_\_\_

Date (dd/mmm/yyyy): \_\_\_\_/\_\_\_\_/\_\_\_\_

Over the last 2 weeks, how often have you been bothered by the following problems?	Not at all sure	Several days	Over half the days	Nearly every day
1. Feeling nervous, anxious, or on edge	0	1	2	3
2. Not being able to stop or control worrying	0	1	2	3
3. Worrying too much about different things	0	1	2	3
4. Trouble relaxing	0	1	2	3
5. Being so restless that it's hard to sit still	0	1	2	3
6. Becoming easily annoyed or irritable	0	1	2	3
7. Feeling afraid as if something awful might happen	0	1	2	3
Add the score for each column	+	+	+	
Total Score ( add your column scores ) = _____				

**If you checked off any problems, how difficult have these made it for you to do your work, take care of things at home, or get along with other people?**

Not difficult at all \_\_\_\_\_

Somewhat difficult \_\_\_\_\_

Very difficult \_\_\_\_\_

Extremely difficult \_\_\_\_\_

Source: Spitzer RL, Kroenke K, Williams JBW, Lowe B. A brief measure for assessing generalized anxiety disorder. *Arch Intern Med.* 2006;166:1092-1097.

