## 5.0 DATA COLLECTION AND RETENTION

The study endpoints data will be collected from each participant's study questionnaires. The data will be collected electronically via the patient's own device, and uploaded to an electronic data capture system. Only patient data from the stratified indication(s) will be used for analysis of symptom response. The data will be used to demonstrate that the Nu-V3 device provides participants with relief of the symptoms of pain, depression, anxiety and/or sleeplessness. The data analysis will include comparative data for each participant's questionnaire prior to beginning treatment with the Nu-V3 device, the participant's weekly questionnaires during

treatment and the questionnaire completed at the end of the treatment with the Nu-V3 device.

Interim analyses of available data will be regularly submitted to the FDA for review.

The Principal Investigator at each site will be responsible for recording, collecting, and storing the research participant's study data. The written records must be stored in a secure location. Only the Principal Investigator or designated study staff will have access to the study records and all electronic files will be password protected. The Principal Investigator will also maintain adequate records for the study including:

- all correspondence with the IRB and Sponsor
- other pertinent data related to the study

All records are to be retained by the Principal Investigator for a period of seven (7) years following the closure of the study. Following study closure, the Principal Investigator shall inform Nu-Life of the location of study records and storage changes (i.e. the Principal Investigator leaves the institution where the study was conducted). In such cases, the study records may be transferred to another institution, investigator, or to Nu-Life upon written agreement between the Principal Investigator and Nu-Life.

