## 8.0 STUDY ENDPOINT and DATA ANALYSIS

### 8.1 Primary Endpoints: Primary endpoints consisted of the following:

Safety: The primary safety endpoint is the occurrence of reported unanticipated problems involving risk to subjects or others (“UPIRTSOs”). These UPIRTSOs are defined as those problems which alter the risks to subjects or others. This includes any study suspensions or holds. The primary safety endpoint analyses will be based on a risk-benefit conclusion.

Effectiveness: The primary effectiveness endpoints are an overall change in median reported symptoms of pain, anxiety, depression, and/or sleeplessness via numeric rating scales at 8 weeks. This primary effectiveness is measured by median reported symptom changes in pain, anxiety, depression, and/or sleeplessness for respective stratified populations via the following validated tools: Pain - Pain Intensity and Interference (PEG\_Scale), Anxiety - Generalized Anxiety Disorder 7-item (GAD-7) scale, Depression - Patient Health Questionnaire (PHQ-9), Sleeplessness - PROMIS short form 4a, and overall improvement of quality of life (QOL) - Patient’s Global Impression of Change (PGIC).

The hypothesis-driven criterion of effectiveness is to show that there is a statistically significant reduction in the median reported pain, anxiety, depression, and/or sleeplessness levels of patients using the Nu-V3 device. The second criterion is intended to show that there is a statistically significant improvement in reported quality of life and perceived treatment benefit, secondary to overall reported symptom reductions of pain, anxiety, depression, and/or sleeplessness.

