## PHQ-9- Patient Health Questionnaire

Subject ID: \_\_\_\_\_ Date (dd/mmm/yyyy): \_\_\_\_/\_\_\_\_/\_\_\_\_

Over the last 2 weeks, how often have you been bothered by any of the following problems?  
(use "✓" to indicate your answer)

	Not at all	Several days	More than half the days	Nearly every day
1. Little interest or pleasure in doing things	0	1	2	3
2. Feeling down, depressed, or hopeless	0	1	2	3
3. Trouble falling or staying asleep, or sleeping too much	0	1	2	3
4. Feeling tired or having little energy	0	1	2	3
5. Poor appetite or overeating	0	1	2	3
6. Feeling bad about yourself—or that you are a failure or have let yourself or your family down	0	1	2	3
7. Trouble concentrating on things, such as reading the newspaper or watching television	0	1	2	3
8. Moving or speaking so slowly that other people could have noticed. Or the opposite — being so fidgety or restless that you have been moving around a lot more than usual	0	1	2	3
9. Thoughts that you would be better off dead, or of hurting yourself	0	1	2	3

add columns  +  +

(Healthcare professional: For interpretation of TOTAL, please refer to accompanying scoring card). TOTAL:

10. If you checked off any problems, how difficult have these problems made it for you to do your work, take care of things at home, or get along with other people?	Not difficult at all _____ Somewhat difficult _____ Very difficult _____ Extremely difficult _____
---	---

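### The zero category on the printed GAD-7 does not answer its 'how often' question, so a score of 0 on the primary anxiety measure is ambiguous (minor)

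*Protocol*

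**What the plan says.** Protocol 8.1 measures the primary effectiveness endpoint at 8 weeks "via the following validated tools", and for the anxiety stratum names "Anxiety - Generalized Anxiety Disorder 7-item (GAD-7) scale". The SAP's Primary Endpoints paragraph names the same tool.

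The form is printed in Protocol Appendix 11, under the title "Complete Patient ePRO Questionnaire Packet". Its stem reads "Over the last 2 weeks, how often have you been bothered by the following problems". There are four response columns, scored 0, 1, 2 and 3 on each of 7 items. The columns scored 1 to 3 are graded frequencies over the two weeks. The column scored 0 is headed "Not at all sure".

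The PHQ-9 in the same appendix has the stem "Over the last 2 weeks, how often have you been bothered by any of the following problems" and heads its zero column *Not at all*.

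Protocol 5.0 limits who enters each symptom analysis: "Only patient data from the stratified indication(s) will be used for analysis of symptom response".

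**The concern.** A frequency question needs a lowest answer that means never. The printed lowest answer says instead that the respondent is not certain. Two misreadings are possible, and they pull in opposite directions:

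- A patient without the symptom avoids the column, because it does not say what they mean, and marks *Several days*. The item is recorded as 1 instead of 0, which would hide improvement.
- A patient who has had the symptom but cannot say how often takes the label literally and marks it. The item is recorded as 0, which would create improvement.

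The same label at every visit does not guarantee that the error cancels. Zero is where an item goes when it resolves, so the ambiguous column should be needed more often at Week 8 than at baseline. Protocol 4.0 describes a single-arm, open-label study, so there is no comparator in which the same error would occur and be subtracted out. Patients answer on their own mobile devices. The visit procedure checks that forms are complete, not how a label was understood.

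**Working it through.** Neither document gives a figure for the GAD-7 (no effect size, standard deviation or sample size), so there is nothing to reproduce. The check is a comparison of the two forms followed by a bound from the printed scoring.

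**Step 1. The two forms side by side (Protocol Appendix 11).**

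| | GAD-7 | PHQ-9 |
|---|---|---|
| Kind of question | how often | how often |
| Recall period | 2 weeks | 2 weeks |
| Column scored 0 | "Not at all sure" | *Not at all* |
| Columns scored 1 to 3 | graded frequencies | graded frequencies |

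The packet labels the same point of the same kind of scale in two ways, and only the PHQ-9 label answers the question asked.

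**Step 2. How much of the score is exposed.** The last item is "7. Feeling afraid as if something awful might happen", so there are 7 items, each scored 0 to 3. The total runs from 7 × 0 = 0 to 7 × 3 = 21. The heading applies to every item, so all 7 are exposed.

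**Step 3. Bound for one patient at one visit.** Assumption, not in the documents: a misread item moves by one step, between 0 and 1. If *k* items are misread in the same direction, the total moves by *k* × 1 points, with *k* from 0 to 7:

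- no item misread: 0 points;
- all 7 misread: 7 × 1 = 7 points, and 7 / 21 = 33% of the scale.

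The upper end needs a patient without any of the seven symptoms to report every one of them on several days. It is a limit, not an expectation.

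**Step 4. What reaches the change score.** Let *a₀* and *a₈* be the numbers of items raised from 0 to 1 at baseline and Week 8, and *u₀* and *u₈* the numbers lowered from 1 to 0. With change taken as Week 8 minus baseline, so that improvement is negative:

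error in change = (*a₈* − *a₀*) − (*u₈* − *u₀*).

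If misreading is equally common at both visits, the error is zero. If only avoidance of the zero column grows as items resolve, the error is positive and improvement is understated. If only marking it out of uncertainty grows, the error is negative and improvement is overstated. The documents give none of the four counts, so neither the sign nor the size can be worked out.

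**Step 5. From patient to endpoint.** The endpoint is a change in the median of whole-number totals. An average shift per patient does not carry over directly to that median, so no figure for the endpoint is offered.

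**The case against.** The strongest reply is that most patients will answer as intended. A 0 is printed for every item in the lowest place of an ordered 0-1-2-3 scale, the label begins with the expected words, and every other column asserts that the symptom was present. This stands. A reader might infer that a symptom-free patient has no correct answer available, but the form does not support that. The answer exists and scores 0; the fault is that the same 0 can also be read as uncertainty.

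A reader might also infer that the instrument has lost its validated status. The form credits a published source, but that source is not in the documents, so a departure from it cannot be shown. The difference from the PHQ-9, which is another instrument, does not show it either.

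The deployed ePRO screen is not shown. The packet's title makes it plausible that the screen carries the same label, but this has to be checked.

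Reach is limited as well, since only the anxiety stratum enters the anxiety analysis. This has less force than it seems. Protocol 3.1 asks only that the patient present with one or more of the symptoms, and neither it nor section 4.0 sets a GAD-7 threshold. Mildly anxious patients with several items truly at zero can therefore enter that stratum.

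**Conclusion.** The labelling fault is real and can be seen on the page. The zero response on all 7 items of the primary anxiety measure is ambiguous, and it is inconsistent with the PHQ-9 in the same packet. In a single-arm design, misreading that becomes more or less common between baseline and Week 8 would pass into the change score. The possible effect per patient is 0 to 7 of 21 points under the one-step assumption, in either direction, and the documents hold no evidence on frequency. They do not support a claim that the anxiety result is biased in a known direction or by a known amount. The conclusion also assumes that the ePRO screen matches the printed form. Severity is minor: the effect is unmeasured and may be small, but a zero recorded under this label cannot be interpreted afterwards, and correcting it is cheap.

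**What to change.** 1. Compare the label with the source instrument and with the deployed ePRO screen.
2. Set the GAD-7 zero label to *Not at all* in the packet and the ePRO build before enrolment, or before further enrolment.
3. If any patients have already answered the present label, keep each of them on one version at least for baseline and Week 8, record the version at each assessment, and report the anxiety result separately by version. Merely excluding patients whose versions differ would not be enough, because patients who used the present label at both visits would stay in both analyses, and theirs is the error in question.

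Cost: an IRB form revision and a version flag in the data. No visits or patients are added. If both versions have been used, each version-specific result rests on fewer patients and is less precise.
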